**CPRS Notes.** After the informed consent process is completed, researchers will enter a Study Initiation Note into the participants' digital medical record. To ensure that mental health staff is aware of patients' participation, the attending psychiatrist and nurse manager of the unit will be added as a signees. They will also be added to MI-SI session noted which will document whether the individual exhibited suicidal ideation, plan, or intent during the session.

Participant Procedures. The study will consist of three phases. Phase 1, the assessment phase (15 min.), will be conducted on day 2 or 3 of hospitalization to confirm eligibility. Eligible participants will immediately complete the baseline assessment of risk factors and outcome variables (50 min.). Phase 2, the treatment phase, will occur between day 2 or 3 and discharge. Participants will be randomized to MI-SI plus TAU or to TAU alone. The MI-SI plus TAU condition will include one or two sessions of MI-SI (50 mins. each) in addition to TAU. Sessions will be held on consecutive days and recorded using a digital audio recorder, which will be coded for clinician fidelity. Phase 3, the follow-up phase, will take place after discharge. Participants in the MI-SI plus TAU condition will complete 1 booster MI-SI telephone session within 1 month of discharge (30-50 min.). All participants will be contacted by telephone to complete follow-up assessments (50 min.) at 1, 3, and 6 months to measure outcome variables and risk factors. Research assistants who are blind to condition will complete follow-up assessments.

Table 3: Complete List of Measures

			Time of Assessment			
Domain	Measure	Purpose	Screen	Baseline	*Follow-ups	**Follow- ups after discharge
Demographics	UAB	Screen				
Veteran Status	UAB	Screen				
Psychotic Disorders	MINI	Screen				
Manic Episode	MINI	Screen				
Cognitive Deficits	MMSE	Screen				
ТВІ	TBI-ID	Screen				
Suicidal Ideation (SI)	SSI	Outcome				
Depression	PHQ-9	Risk Factor				
PTSD	PCL-C	Risk Factor		$\sqrt{}$		
Anxiety	BAI	Risk Factor		$\sqrt{}$		$\sqrt{}$
Alcohol Use	AUDIT	Risk Factor		$\sqrt{}$		$\sqrt{}$
Drug Use	DAST-10	Risk Factor		$\sqrt{}$		
Substance Use	SUF	Risk Factor		$\sqrt{}$		$\checkmark$
Frequency						
Substance Problems	InDUC	Risk Factor		V		V
Insomnia	ISI	Risk Factor		V		$\sqrt{}$
Anger	LHA	Risk Factor		V		
Suicidal Behavior	C-CSSRS	Risk Factor		V		V
Contemplation Ladders	CL	Risk Factor		√	$\sqrt{}$	$\sqrt{}$
Treatment Engagement	TSR	Outcome		√		$\sqrt{}$

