- 6. TBI (7 items): The Ohio State TBI-ID short form is a valid and reliable screen for TBI. TBI-related dementia will be identified by positive screen for moderate to severe TBI and a score of 26 or lower on the MMSE, the conservative cutoff point for the MMSE. 
- 7. Suicidal Ideation (SI): SI will be measured with the Scale for Suicidal Ideation (SSI)  $^{27}$ . The SSI is an interview that measures the "intensity of the patient's specific attitudes, behaviors, and plans to commit suicide" (p. 4).  $^{44}$  Participants will be asked about "current" suicidal ideation defined as occurring during the past week (SSI-C),suicidal ideation at its "worst point" in the patient's life (SSI-W) at baseline, and "acute" suicidal ideation in the last 48 hours. The SSI is considered the gold standard measure for SI, has been found to have good internal consistency ( $\alpha = 0.84$ ), construct validity,  $^{52}$  and predictive validity as scores over 2 are predictive of suicide,  $^{3}$  and has been used with Veterans.  $^{53}$  The SSI-C will be used to measure SI the week prior to admission to obtain an accurate measure of SI during the period of acute risk that preceded hospitalization, and to avoid underestimating the severity of SI due to the benefits of hospitalization. The SSI-C is sensitive to change over time in adult clinical samples and will also be used to assess the severity of SI at follow-up assessments.  $^{3}$

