**In-Hospital Follow-ups.** These assessments will be conducted 2-3 days and 3-5 days after the baseline assessment, during the course of hospitalization. If patients are discharged during this time, only the first follow-up will be obtained. Participants will be asked to complete a "modified" SI that assesses suicidal ideation over the past 48 hours to assess recent change , Contemplation Ladders and the PDM. When it is time to conduct the in-hospital follow-up assessment, a researcher on the unit will call a researcher at the CoE who will conduct the assessment by telephone. This will ensure that outcome assessments are conducted by researchers who are blind to condition.

**Post-Discharge Follow-ups.** Follow-up assessments will be conducted at 1, 3, and 6 months via telephone. A telephone follow-up will enable us to expand the catchment area and assess

participants who are hospitalized or in residential treatment and unable to return to the medical center. Procedures will include mailing participants the assessment measures to ease administration. There is precedence for this strategy, as the telephone administered SSI was the primary outcome for the PROSPECT trial, supporting use of the method.  In addition to the SSI, we will also use all risk-factors measures that are used at baseline including the PHQ-9, PCL-C, BAI, AUDIT, DAST-10, SUF, InDUC, ISI, C-SSRS, Contemplation Ladders, HCCQ, TSRQ, PCQ, PDM as well as the exploratory outcome measure the TSR-6 (Table 3). The window for each assessment will open at the midpoint between the previous assessment and the current assessment, and close at the midpoint between the current assessment and the following assessment (e.g., open two weeks before month 1 and close at the end of month 2, the midpoint between 1 and 3 month assessments), and close 3 months after the 6-month follow-up.

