### **Aim 3:** To evaluate improvements during hospitalization.

Exploratory Hypothesis 3: Participants who receive MI-SI plus TAU will report greater reductions in SI during hospitalization, than participants who receive TAU alone.

Exploratory Hypothesis 4: In participants who receive MI-SI plus TAU, in-session living talk will be positively associated with reductions in SI during hospitalization.

Exploratory Hypothesis 5: In participants who receive MI-SI plus TAU, in-session suicide talk will be negatively associated with reductions in SI during hospitalization.

Exploratory Analyses 3-5: Data will be analyzed using GLMM to account for repeated measures within subjects  with a focus on within subject decreases in SI (assessed with SSI scores). A minimum of two GLMMs will be used to examine the effect of MI-SI on the severity of SI at 2-3 and 3-5 days after the baseline assessment, the strength of in-session living and suicide talk and the severity of SI at 2-3 and 3-5 days after the baseline assessment. We will also examine the associations between in-session living and suicide talk on the severity of SI over 1, 3, and 6 months follow-up.

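### The in-hospital SSI is timed from baseline rather than from the MI-SI sessions, so the first score in particular can rate ideation from before or between sessions; this matters most for Hypotheses 4 and 5

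*Combined protocol and SAP*

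**What the plan says.** All references are to the combined protocol and SAP.

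- **Assessment timing** (General Procedures, In-Hospital Follow-ups): "These assessments will be conducted 2-3 days and 3-5 days after the baseline assessment, during the course of hospitalization". The instrument is a modified SSI that "assesses suicidal ideation over the past 48 hours to assess recent change". A patient who is discharged in this period contributes only the first of the two scores.
- **Treatment timing** (General Procedures, Participant Procedures): "Phase 2, the treatment phase, will occur between day 2 or 3 and discharge". Screening and baseline are done on hospital day 2 or 3 as well. Patients in the experimental arm get either one inpatient session or two. On their spacing the protocol states: "Sessions will be held on consecutive days and recorded using a digital audio recorder".
- **Analysis** (Analytical Plan, Aim 3, Exploratory Analyses 3-5): GLMMs relate MI-SI to SI at both in-hospital visits, and also relate "the strength of in-session living and suicide talk and the severity of SI at 2-3 and 3-5 days after the baseline assessment". Talk is further related to SI at 1, 3 and 6 months.
- **Starting value** (Screening Assessment, item 7): "The SSI-C will be used to measure SI the week prior to admission", chosen so that the early benefit of admission does not hide the severity of the crisis. The same item lists an acute SSI covering the last 48 hours. The Aim 3 text does not say which of these defines a reduction.
- **Status** (Analytical Plan, Data Preparation): the exploratory hypotheses are not powered.

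**The concern.** The assessment clock starts at baseline and the treatment clock starts at session 1. No section ties one to the other. A score collected after a session can still describe hours before it, because it looks back two days.

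For Hypothesis 3, any pre-session time inside the look-back is time in which MI-SI could not have acted, so the difference between arms should shrink.

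Hypotheses 4 and 5 are more exposed. They are tested within the MI-SI arm only, and they read talk as a predictor of later reduction in SI. If the rated ideation comes before the talk, the order is reversed: a patient whose ideation has already eased may simply talk more about living.

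The unspecified starting value adds to this. If a 48-hour inpatient score is subtracted from a pre-admission past-week score, the fall that follows admission is counted as change during treatment. Pilot Study #1 paired the measures in this way: past-week SSI at baseline, 48-hour SSI at post-treatment, means 27.56 and 11, effect size (27.56 - 11) / 4.88 = 3.39.

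**Working it through.** The plan gives no figure for this point, so there is none to reproduce. The check is interval arithmetic.

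**Inputs from the document.** First assessment at day f, with f between 2 and 3 after baseline; second with f between 3 and 5; look-back of 2 days; two sessions about 1 day apart.

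**Assumptions.** The day of session 1 is not given, so four cases are shown. Assessments are taken as spread evenly over their windows.

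**Formula.** The look-back runs from f - 2 to f. The share of it before a session at day s is

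b(s, f) = max(0, s - (f - 2)) / 2, capped at 1.

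The look-back lies wholly after the session when f is at least s + 2.

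**Sessions on days 1 and 2.**

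- First score, before session 1: (3 - f)/2 falls from 0.50 at day 2 to 0 at day 3; mean 0.25.
- First score, before session 2: (4 - f)/2 falls from 1.00 to 0.50; mean 0.75. Wholly after session 2 would need f of at least 4, so no first score qualifies.
- Second score, before session 2: (4 - f)/2 falls from 0.50 to 0 over days 3 to 4 (mean 0.25) and is 0 over days 4 to 5. The overall mean is 0.125, and half the scores are wholly after.

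**All cases** (average share of look-back; the share before session 2 includes the time before session 1):

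| Sessions on days | First: before S1 | First: before S2 | First: wholly after S2 | Second: before S1 | Second: before S2 | Second: wholly after S2 |
|---|---|---|---|---|---|---|
| 0.1 and 1.1 | about 0% | 30% | 0% | 0% | about 0% | 95% |
| 1 and 2 | 25% | 75% | 0% | 0% | 12.5% | 50% |
| 1.5 and 2.5 | 50% | 94% | 0% | 3% | 28% | 25% |
| 2 and 3 | 75% | 100% | 0% | 12.5% | 50% | only at day 5 |

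The first row stands for session 1 on the baseline day.

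**One session only.** If it is on the baseline day (day 0), every look-back is wholly post-session. If it is on day 1, the first look-back is 50% post-session at day 2 and 100% at day 3, and the second is always 100%.

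**Who has only the first score.** The average stay was 9 days (Treatment Setting). Baseline on hospital day 2 or 3 puts day 5 after baseline at hospital day 7 or 8, so a patient with an average stay would have both scores. Patients who leave early keep only the more exposed one. In Pilot Study #1, 3 of 16 eligible patients left before session 1, and 9 of the 13 treated completed both sessions.

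**The case against.** The strongest reply has four parts.

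**The second visit is largely clear.** With sessions on days 0 and 1, a second score at any point from day 3 to day 5 looks back only on post-session time. With sessions on days 1 and 2, this holds from day 4. This stands. A reader might infer that the in-hospital SSI cannot serve as an outcome for Hypotheses 3 to 5; the schedule does not support that.

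**The size depends on an unstated lag.** The envelope is opened after the baseline assessment and the therapist is then told (Randomization), so a session on the baseline day fits the text. This stands, and it is why the result is a range. A reader might also infer that much of the rated period always precedes treatment; at day 3 with sessions on days 0 and 1, none of it does.

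**Hypothesis 3 is a randomized comparison.** It concerns reductions during the hospital stay, and both arms are assessed on the same schedule. This stands: the overlap weakens the contrast but does not bias it in favour of either arm. Nor does a common past-week starting value bias it.

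**Hypotheses 4 and 5 claim association only, and talk is also related to later SSI scores.** The 1-, 3- and 6-month associations are indeed free of this problem. The in-hospital hypotheses, however, concern talk and a reduction in SI, and Study of Speech presents talk as a pathway and possible predictor of outcome, so order matters. It is also true that a look-back rule does not remove confounding: patients already improving may talk differently whatever the window. The rule secures temporal order, and a like-for-like starting value adjusts for part of the rest.

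**Conclusion.** The concern holds in a limited form. The first in-hospital score can overlap the period before or between sessions, and nothing in the plan prevents it. On average 25% of its look-back precedes session 1 and 75% precedes session 2 if sessions fall on days 1 and 2. The figures are about 0% and 30% if session 1 is on the baseline day, and higher if sessions start later. The second score is mostly or wholly post-session unless sessions start late.

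These are shares of time, not sizes of bias. The document does not say whether the 48-hour SSI rates average, worst or latest ideation, so the loss of effect cannot be computed.

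For Hypothesis 3 the consequence is dilution. For Hypotheses 4 and 5, temporal order is not assured, with no control arm to compensate. Separately, the starting SSI for all three needs to be named. Hypotheses 3 to 5 are exploratory, and the primary outcome at 1, 3 and 6 months is untouched, so this is an inexpensive improvement to secondary material rather than a threat to the trial.

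**What to change.** Amend the text of Exploratory Analyses 3-5 as follows.

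1. **Record the date and clock time** of each MI-SI session and each in-hospital assessment. Dates are already to be spoken at the start of each audio recording, so only the clock time is new.
2. **Hypotheses 4 and 5, in-hospital analyses:** use as outcome only SSI scores whose 48-hour period begins after the coded session (after the last one, if talk from two sessions is combined). Report the analysis of all scores as a sensitivity analysis.
3. **Hypotheses 3 to 5:** use the 48-hour acute SSI listed in Screening Assessment item 7, taken at screening/baseline, as the starting value or covariate instead of the past-week SSI-C. Item 7 is loosely worded, so state explicitly that this version is collected at that visit.
4. **Hypothesis 3:** keep both time points and all available data, report the effect separately at each visit, and describe the day 2-3 score as an early measure that can overlap pre-treatment time. Resting the hypothesis on late scores alone would drop patients discharged earlier and make the comparison conditional on length of stay after randomization.

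**Cost.** No new measure or visit is needed. Fewer scores qualify for Hypotheses 4 and 5: with sessions on days 1 and 2 and talk coded from session 2, no first scores and about half of second scores would. Those analyses were unpowered already, so the loss is in precision of estimates that were to be read as exploratory.

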Maintaining Blind Outcome Assessments. In-hospital and post-discharge follow-up assessments will be conducted by research assistants who are blind to condition. The blind will be maintained by having research assistants who are not involved in the baseline and treatment phases of the study conduct the assessment by telephone from the CoE. After each outcome assessment, research assistants will be asked if they thought the participant was assigned to the experimental condition (MI-SI plus TAU), control condition (TAU alone), or don't know which condition the participant was assigned to. They will also be asked how they decided the condition to ensure that the blind was indeed broken and the determination was not due to extraneous information such as positive outcome, which would presumably lead a research assistant to guess the MI-SI plus TAU over TAU alone. If blinding was successful, research assistants will not be able to determine assignment at a better than chance rate. 

Randomization. Prior to randomization, participants will be stratified by SSI scores to increase the probability of balanced assignment, which may decrease the probability of a Type 1 error and increase power.  Stratification will be based on a median split using data from pilot study #1. Participants who score below 24 will be in the lower SSI group, and those who score 24 and above will be in the higher SSI group. A blocked randomization procedure using block sizes of 4 and 6 participants will also be used to assure no significant imbalance between the numbers of participants in each condition at any time, and to protect against guessing condition assignment.  Randomization will occur prior to the start of the trial and the results will be recorded in sealed envelopes. After the baseline assessment, the researcher will choose the next envelope (within the strata and block) to determine the participant's assignment. The researcher will then inform the study therapist that a participant has been randomized to receive MI-SI.

**Treatment Conditions.** Participants will be randomized to MI-SI plus TAU or TAU alone.

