Initial Training. The PI will provide initial training in the detailed interview-based measures. In this initial training, all staff will also receive training in the safety procedures (described in the patient safety section). The interviews contain three measures that require extensive training and supervision to achieve consistency of administration and scoring: SSI, TSR, and C-SSRS. Training for these measures will make use of lectures to learn about the measures and role-plays to reach proficiency. The PI will observe research assistants' first two research interviews to ensure that they are using the instruments appropriately and provide corrective feedback. If indicated, interviews will be observed until proficiency is reached. Training and supervision for each measure are included below. All administrations will be recorded and random samples will be independently coded for reliability. Researchers will use digital recorders on the unit, and earbuds that plug into the recorders for telephone assessments.

SSI training: [name] has received training from the developers of the SSI, used it extensively, and trained the PI in its administration and scoring. The PI will provide two hours of training for the research assistants.

TSR training: The PI has used the TSR in both pilot studies that were conducted with high-risk Veterans. Research assistants will receive two hours of training for the measure.

C-SSRS training: The PI has received training in the administration and scoring of the C-SSRS from [name], the developer of the measure. He will provide two hours of training in the C-SSRS for the research assistants.

Weekly Supervision. The PI will provide weekly supervision for the research assistants and lead a monthly half-day meeting in Canandaigua. The agenda will include a review of participant flow including recruitment, scheduling, and retention of subjects; issues pertaining to administration, scoring, entering, and storing interview protocols; subject safety issues; consensus meetings for SSI ratings; consensus meetings for chart reviews; discussion of adverse events; and on a quarterly basis, reviewing the quality of data gathered. Research assistants will also review one another's interview packets for completeness and errors at these meetings.

**MI-SI Training and Supervision.** MI-SI will be delivered by masters and doctorate-level research clinicians who will have received specialized training and supervision.

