MI-SI Training. Training will consist of sixteen hours. It will consist of 8 hours of training in general MI followed by eight hours of MI-SI training. Training modalities include listening to power-point presentations, selected readings from the MI text  and the MI-SI manual (included in Appendix), MI exercises, and listening to and discussing recorded examples of MI-SI. The PI will observe the first two interviews to ensure that therapists meet MITI fidelity criteria and provide corrective feedback. Additional training activities will be scheduled as necessary.

MI-SI Supervision. An RCT evaluating methods for training MI clinicians found that ongoing coaching and/or feedback is needed to maintain proficiency in MI.  The PI will provide weekly supervision for MI-SI clinicians, focusing on promoting the fidelity of MI-SI by discussing

difficult cases, listening to and discussing recorded MI-SI interviews, and reviewing MI materials and publications.

**Interview Coding and Training.** MI-SI sessions will be recorded and coded for fidelity using the MITI,  which requires specialized training.

MITI Coding and Training. The MITI is a behavioral coding system that is used to code 20-minute samples of tape for adherence to MI principles (e.g. empathy, autonomy support) and use of specific MI techniques (e.g. reflections, open questions). Summary values from coded interviews will be used to assess fidelity,  and provide material for supervisory sessions. A random selection of interviews will be double-coded and inter-rater reliability will be computed using inter-class correlation coefficients. 

The PI will provide MITI training to the research assistants who are coding the MI-SI therapy sessions. The protocol that will be used is identical the one use by [name]., an MI Training expert who trained coders for Project MATCH,  and trained the PI. Training will consist of eight hours and include reviewing the MITI coding scale, coding MI interviews and comparing the codes to "gold standard" codes available on the MI website,  and coding recordings of MI-SI interviews. Coders will be considered reliable when they achieve reliabilities of good or better (ICC > .60) on 80% of MITI codes. 

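### SSI ratings are scheduled for consensus in meetings led by the PI, who also supervises MI-SI therapy, and no rule fixes the blinded assessor's follow-up score first

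*Combined protocol and SAP*

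**What the plan says.** The SSI is described as an interview (Screening Assessment, item 7), and its severity at 1, 3 and 6 months is the primary outcome (Primary Analysis 1).

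On blinding, Participant Procedures says: "Research assistants who are blind to condition will complete follow-up assessments". Maintaining Blind Outcome Assessments says: "In-hospital and post-discharge follow-up assessments will be conducted by research assistants who are blind to condition". These assistants take no part in baseline or treatment, work by telephone from the Center of Excellence, and record after each assessment which arm they think the participant is in and why.

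On supervision of the research assistants, Weekly Supervision says: "The PI will provide weekly supervision for the research assistants and lead a monthly half-day meeting in Canandaigua". The agenda includes "consensus meetings for SSI ratings; consensus meetings for chart reviews; discussion of adverse events". It adds: "Research assistants will also review one another's interview packets for completeness and errors at these meetings". Initial Training says: "All administrations will be recorded and random samples will be independently coded for reliability".

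On supervision of the therapy, MI-SI Supervision says: "The PI will provide weekly supervision for MI-SI clinicians". The methods include "listening to and discussing recorded MI-SI interviews".

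On the data path, the Data Entry paragraph has a colleague edit the completed packet, after which the interviewer enters the data. It mentions neither a consensus step nor a locked score. The Adverse Events paragraph takes the decision on what counts as an adverse event away from the PI, to limit bias. There is no counterpart for the SSI.

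**The concern.** Participants and therapists know the arm. For an outcome that an interviewer scores, masked rating is therefore the main protection against expectation entering the score. The plan builds that protection around the interview, then schedules a later step in which SSI ratings are discussed to agreement under someone who follows the experimental therapy case by case. If follow-up scores are settled there, someone likely to know the arm can influence them.

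The plan's own check on the blind would not detect this. The arm guess is recorded after each assessment, so it captures what the assessor knew at that time. It says nothing about a score altered later in a meeting. Independent coding of recordings applies to random samples, and the plan does not say whether those coders are masked or whether their ratings affect the score of record.

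**Working it through.** **1. Tracing a follow-up SSI score through the plan.**

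| Step | Where | Masking stated? |
|---|---|---|
| Interview and scoring by telephone | Maintaining Blind Outcome Assessments; In-Hospital and Post-Discharge Follow-ups | Yes, for the assistant who conducts it |
| Arm guess recorded | Maintaining Blind Outcome Assessments | Tests that assistant's blind after the assessment |
| Independent coding of a random sample | Initial Training | Not stated |
| Consensus on SSI ratings, led by the PI | Weekly Supervision | Not stated |
| Packet review among assistants in the same meetings | Weekly Supervision | Not stated |
| Packet edited by a colleague, then entered | Data Entry | Not stated; no lock, no rule to keep the original score |

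The plan does not say whether the colleague's edit before entry is the packet review held in the meetings. If it is, entry follows the meeting. If it is not, the order of entry and consensus is open.

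**2. Does the PI know the arm?** This is an inference. Only MI-SI participants have therapy sessions to supervise, so hearing a recording or discussing a case identifies that participant's arm. How many cases the PI would recognise at an SSI meeting is not stated.

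**3. How many ratings could be involved.** The Participants section sets aside up to 28 of 140 for training and piloting, which leaves 140 − 28 = 112 for the trial, the figure used in the Power Analysis. (Aim 1 speaks of a trial of 140.)
- Post-discharge, primary outcome: 112 × 3 = 336 at most.
- In hospital, exploratory: 112 × 2 = 224 at most. The second is not obtained if the patient has left the unit.
- Minimum for both: 0, if consensus is for calibration or for baseline ratings only.

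The maxima count every scheduled follow-up rating with no losses. They are ceilings on exposure.

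**4. What a shift would do (illustration only).** The inputs are those of the Power Analysis: SD 8.4, correlations .50 and .70, one baseline and three follow-ups, 45 per arm, change scores.
- SD of change = 8.4 × √[(1 + 2 × .70)/3 + 1 − 2 × .50] = 8.4 × √.80 = 7.513.
- SE = 7.513 × √(2/45) = 1.584.
- The plan's one-sided powers for 5, 4 and 3 points are .94, .81 and .60. These inputs give .935, .811 and .598, so the stated figures reproduce closely.

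Now assume no true effect and a shift of *b* points in favour of MI-SI in the between-arm difference. One-sided type I error is Φ(*b*/1.584 − 1.645): .050 at *b* = 0, .092 at 0.5, .155 at 1 and .351 at 2. The documents give no value for *b*, and zero is possible. The calculation uses the plan's change-score approximation, not its Poisson mixed model.

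**The case against.** The strongest reply is that the agenda item is rater calibration. It sits under Research Assistant Training and Supervision, whose purpose is standardization, and checking packets for completeness and errors is ordinary quality control. The Data Entry paragraph has no consensus step, so on its face the interviewer's own score is what is entered. The blinding rule is explicit and makes no exception for discussions of scoring. Calibration is a fair reading, and on it no follow-up rating is affected.

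What remains is that the agenda names ratings, not training examples, and the same meetings handle trial packets and chart-review consensus. Silence in Data Entry does not settle whether a score may be revised before or after entry.

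A reader might go further and infer that a consensus score replaces the blinded one, that the PI decides it, or that the blind is broken. The documents say none of these things. Nor do they support a second route through the 6-month chart review: they do not say that the blinded assessors carry it out, or whether the booster session is charted.

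**Conclusion.** The concern holds as a gap in the protection of the primary outcome: the plan schedules consensus on SSI ratings under a PI who probably knows some allocations, and no rule fixes the blinded assessor's follow-up score first or names the score to be analysed. Followed as written, the plan permits influence at that step; it does not show that any occurs. The exposure is 0 to 336 post-discharge ratings, plus 0 to 224 in hospital. The upper ends assume that every follow-up rating is taken to consensus, which the text does not say.

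No bias can be quantified, and the type I error figures show sensitivity to an assumed shift only. The conclusion rests on one inference, that supervising MI-SI cases and recordings reveals allocation. The point should be settled before follow-up data accrue, because a score changed without a record cannot be recovered later.

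**What to change.** Add to Weekly Supervision and Data Entry:
- Each blinded assessor's in-hospital and post-discharge SSI score is entered and locked before any meeting, and is the score analysed.
- Later corrections of errors are logged and the original is kept.
- SSI consensus meetings are for calibration only; or, if trial participants' follow-up ratings are discussed, this is done from the recordings after the lock, without disclosing arm, and does not alter the score of record.

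The cost is minor procedural work and the loss of consensus as a means of changing a score. No visits, measures or recordings are added, since all administrations are already to be recorded. Sample size and power do not change. Barring the PI from these meetings is not needed: once the score is locked it would add little, and the PI is the person who trains the assistants on the SSI. Supervision on participant risk and adverse-event reporting are outside this change.
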